Few prospective comparative studies (Hurzeler & Weng, 1999; Griffin, 2006; Wessel&Tatakis, 2008) reported greater incidence of post-operative pain for DGG compared to CTG procedures, except for cases with necrosis or dehiscence of the primary flap.

However, limits of these studies are due to lack of data about dimensions of grafts harvested from the palate.

Zucchelli & co-authors 2010 demonstrated that post-operative morbidity after CTG and DGG techniques doesn't show statistically significant differences; factors that influence post-surgical consumption of pain killers are not the type of healing (primary or secondary) of the palatal wound, but the height and depth of the graft harvesting.

Furthermore, CTG techniques increase surgical time (Zucchelli, 2010) which is related to post-surgical pain (Cortellini, 2009; Griffin, 2006).

Since 1988 platelets concentrates have been proposed in several medical fields with the aim of improving wounds healing and reducing post-operative morbidity.

In dentistry only few authors investigated the use of platelets concentrates on palatal donor sites after connective tissue graft harvesting (Shayesteh, 2012; Yen, 2007) and none of them used L-PRF (Leucocyte and Platelet Rich Fibrin) (Choukroun, 2006; Giannini 2015).

The aim of this study is to evaluate complications and post-operative morbidity in patients that undergo epithelium-connective graft harvesting from palate with or without the use of autogenous PRF membranes for covering the donor site wound.

Material and methods

42 subjects were selected from those seeking care at the Department of oral surgery, Dental clinic G.Vogel, San Paolo hospital, Milan.

The study protocol, questionnaires and informed consent, in full accordance with the ethical principles of the Declaration of Helsinki of 1975, as rivisited in 2000, received the approval by the local ethic committee. All patients agreed to participate in the study and signed a written informed consent according to the above-mentioned principles.

All participants met the study inclusion criteria: age range 18-60 years,

- FMPS and FMBS < 20%,
- presence of two adjacent Miller's Class I and II recession defects on natural teeth (≥ 2 mm in depth);
- periodontally and systemically healthy;
- controindications for periodontal surgery
- taking medications or having deseases known to interfere with periodontal tissue health or healing and coagulation.
- Subject smoking more than 10 cigarettes a day
- Gingival recessions on molar teeth were excluded.

Study design

The study was a double-blinded, randomized-controlled clinical trial with a parallel design. The technique of covering the palatal wound with PRF membranes (Test Group) was compared with the use of hemostatic agents with oxidized and regenerated cellulosa (control group).

The study protocol involved a screening appointment to verify eligibility, surgical therapy, evaluation of patient morbidity 2 weeks after surgery, post-operative clinical evaluation 3,14,30 and 90 days after the surgery.

Sample size and randomization

To obtain a statistical power of 80% , $\alpha = 0,05$ and $\beta = 0,8$ were used, considering the previous randomized comparative study (Wessel&Tatakis, 2008) that had patient morbidity as the primary outcome.

As a minimum, 18 patients per treatment arm would have been required.

Patients were assigned to one of the two treatment groups using a computer-generated randomization table. Allocation concealment was achieved using two sealed coded opaque envelope containing the treatment of the specific subject.

The operator responsible of the blood collection (BC) was not part of the surgery team.

Before surgery the BC opened the first envelope determining the Group of the patient: blood collection, for preparing the platelets concentrate, took place only in Test Group.

Whereas the surgeons opened the second envelope only after the graft harvesting, before suturing.

Principal evaluated outcomes

The patient morbidity was evaluated with a questionnaire given to patients 1 week following surgery considering parameters such as post-operative pain, discomfort, bleeding, stress and inability to chew. The questionnaire included the evaluation of the intensity of these parameters on a visual analogical scale (VAS) of 100 mm (Hjermstad, 2011). Discomfort was defined as the level of soreness experienced by the patients during the first post-operative week due to the palatal wound and how it influenced the ability to work and the quality of the sleep.

Bleeding was considered to be the prolonged hemorrhaging during the post-surgical week reported by the patient. Stress was related to the level of apprehension and fear experienced by the patients of jeopardizing the palatal wound. Inability to chew was described as the level of variation of the patients' eating habits due to the presence of the palatal wound.

Patients were asked also to evaluate the pain related to the palatal wound and the pain related to the grafting site, determining how much they can discriminate them.

Post-operative pain was also indirectly evaluated on the basis of the mean consumption (in mg) of analgesics (Ibuprofen). A closed box of pills was given to the patients recommending them to bring it back at the control visits allowing to count the number of consumed pills.

A blind operator evaluated clinical healing of the donor site 3,14,30 and 90 days after surgery. Sutures removal took place after 2 weeks. At any control visit photos of the palatal sites were taken and any complication such as marginal tissue necrosis, hematoma, infection, sensibility disorders was recorded.

Secondary outcomes

- Surgical chair time was measured in both groups using a chronometer from the first incision to the last suture.
- Evaluation of the thickness of the epithelium-connective tissue graft that was withdrawn and estimate the thickness of the residual connective tissue in the donor site. A preliminary measurement was performed by using a needle with a silicon endodontic stop which pass through 5 holes of a standardized template which allowed to obtain the mean thickness of the palatal fibromucosa

The measurement was then repeated in the same 5 points on the withdrawn graft in order to obtain the mean thickness of the graft and indirectly the thickness of the residual tissue in the palatal donor site.

PRF Protocol

Venous blood was collected with a butterfly needle in two 10 mL tubes (Venosafe ref: VF- 109SP, Venosafe™, Teramo, Roma, Italia) without anticoagulants or other chemicals. The tubes were immediately centrifuged at 3000 rpm for 10 minutes (Hettich Zentrifugen EBA 20 - HETTICH ITALIA SRL - [name]).

At the end of centrifugation a fibrin clot (PRF) was obtained in the middle of the tube, just between the red corpuscles at the bottom and acellular plasma at the top. The PRF clot was taken from the tube (Fig.3) and the red cells portion at the base of the clot was eliminated with sterile scissors (Fig.4) Then the PRF was enveloped in sterile gauzes and positioned between two glass plates: the compression drove out the serum from the clot obtaining PRF membranes (Fig.5) that were ready to be used in the surgical site (Fig.6).

Surgical techniques

After local anesthesia with Mepivacaine 2% + Adrenalin 1 : 100.000, bilaminar (CAF + CTG) technique was performed in both patient groups to accomplish root coverage.

Donor site and receiving site were contralateral, in this way the patient could more easily distinguish the pain related to the two surgical areas.

The connective harvesting was realized with the help of a single-use rectangular template with standardized dimensions 20 x 6 mm and 5 holes which permitted the measurement of the thickness of palatal fibromucosa in five repeatable points (Fig.1)

Standardized dimensions of the template were obtained estimating the average amount of CTG needed for the treatment of the types of gingival defects included in the study.

The template was kept adherent to the palatal mucosa in the premolar-molar area for guiding the incisions needed for the graft harvesting; the first incision was realized 1-1,5 mm apical to the gingival margin of the adjacent tooth.

The thickness of the graft was maintained uniform during the withdrawal. Once the graft was separated, the template permitted to repeat the measurements of thickness through its five holes (Fig.2). Then the disepithelization was performed using a 15C blade.

The exposed roots surfaces were then covered by the connective grafts which were sutured to the remaining soft tissue of interdental papillae.

The graft was covered by the coronally advanced flap which was sutured with sling sutured ancore around the palatal cingulum of teeth with gingival recessions.

The surgeons were then informed of which type of palatal wound covering to perform by opening the labelled envelope, which contained the patient's number with the assigned treatment.

In the Control Group hemostatic agents with oxidized and regenerated cellulosa (TABOTAMP; Ethicon Sarl. [name]) were sutured to the palatal wound with mattress suture (silk 5/0).

In the Test Group the same suture technique was used for covering the donor site with PRF membranes (Fig.6).

Post-surgical protocol

All the patients were treated with amoxicillin + clavulanic acid 2g 1 hour before surgery and 1g 6 hours after, then the therapy continued for 5 days with 1g every 12 hours.

In case of penicillins allergy, patient received clarithromycin 500mg 1 hour before surgery and 250mg 6 hours after, then 1 dose every 12 hours for 5 days.

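### The double-blinded label is not supported for the patient, who rates or drives every outcome tested in the SAP

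*Protocol*

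**What the plan says.** The Study design section of the Protocol gives the label: "The study was a double-blinded, randomized-controlled clinical trial with a parallel design". It assigns the label to no role.

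The Sample size and randomization section describes two envelopes. The blood-collection operator opens the first before surgery, and "blood collection, for preparing the platelets concentrate, took place only in Test Group". The same section adds: "The operator responsible of the blood collection (BC) was not part of the surgery team". On the second envelope it says: "Whereas the surgeons opened the second envelope only after the graft harvesting, before suturing".

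The PRF Protocol section describes the draw itself: "Venous blood was collected with a butterfly needle in two 10 mL tubes". Under Surgical techniques, the only anaesthesia mentioned is local.

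Two roles are called blind. Under Principal evaluated outcomes: "A blind operator evaluated clinical healing of the donor site 3,14,30 and 90 days after surgery". In the SAP, the person running the analysis is also described as blind.

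The Material and methods section records that patients "signed a written informed consent according to the above-mentioned principles". The text of that consent is not part of the documents available for this review.

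**The concern.** Blinding protects an outcome only if it covers whoever produces that outcome. Here the morbidity questionnaire is completed by the patient, and after the dose given at the start of surgery the patient decides whether to take more ibuprofen. A reader who meets the double-blinded label may well take it that patient expectation was controlled in the comparisons reported. The procedures described do not establish that. At stake is how far differences in pain, discomfort, stress, chewing, bleeding or analgesic use can be attributed to the PRF membrane rather than to what patients believed they had received.

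**Working it through.** No formula applies. The check sets what is described for each role beside who determines each tested outcome.

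**Step 1. Masking described, by role**

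- Blood-collection operator: knows the allocation from before surgery (Sample size and randomization).
- Surgeons: unaware during harvesting, then informed before the palatal wound is covered (Sample size and randomization; Surgical techniques).
- Donor-site healing evaluator: called blind (Principal evaluated outcomes).
- Data analyst: called blind (SAP, Data analysis).
- Patient: no statement. Keeping the blood-collection operator out of the surgical team and delaying the second envelope both shield the surgeons. Neither is directed at the patient.

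**Step 2. What the patient experiences**

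A Test patient has two tubes of 10 mL drawn (2 × 10 = 20 mL) before surgery; a Control patient has none. The only anaesthesia described is local. Nothing in either document describes an equivalent draw in controls, a way of hiding the draw, or an instruction to keep the allocation from patients. The arms therefore differ in a step that the patient can notice.

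**Step 3. Comparisons named in the SAP**

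| Comparison | Test | Who determines the value |
|---|---|---|
| Ibuprofen (mg) | t-test | Patient decides on intake; pills are counted |
| Donor-site pain | Mann-Whitney | Patient VAS |
| Grafting-site pain | Mann-Whitney | Patient VAS |
| Discomfort | Mann-Whitney | Patient VAS |
| Inability to chew | Mann-Whitney | Patient VAS |
| Stress | Mann-Whitney | Patient VAS |
| Bleeding | Mann-Whitney | Patient VAS |

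Count: 1 t-test + 6 Mann-Whitney tests = 7. All 7 are patient-rated or patient-driven. Donor-site healing, the principal outcome with a blind assessor, has 0 named tests.

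**Step 4. Are the 7 equally exposed?**

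No. Grafting-site pain concerns the recipient site, where both arms receive the same root-coverage procedure; donor and recipient sites are on opposite sides so that patients can tell the two pains apart. Expectation about the palatal covering bears on it less directly. For ibuprofen, the Protocol says: "A closed box of pills was given to the patients recommending them to bring it back at the control visits". Counting the returned pills makes the measurement more objective, but the decision to take a pill remains the patient's.

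**The case against.** The strongest reply is that the deciding fact cannot be seen. A draw reveals the arm only to a patient who knows that the membrane is made from their own blood and that controls are not bled. An ethics committee approved the consent and patients signed it; what it told them is unknown. This stands, and it limits the claim to: patients may be able to infer their arm.

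A second reply is that the label may mean evaluator plus analyst. It may, but neither person gives a VAS score or decides on a dose, so that reading leaves every tested comparison without a blind rater.

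A third reply points to protective features. Controls receive an active covering fixed with the same suture technique, pills are counted, and the identically treated grafting site offers a partial internal comparator, since a general reporting shift might show there too. These points deserve credit. They do not conceal a draw that has already taken place, and expectation might act on the palate alone.

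A reader might go further and infer that patients were in fact unblinded, or that the results are biased in favour of PRF. The documents support neither. They do not show what patients knew, and because both arms have a sutured covering, even the direction of any expectation effect is open.

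**Conclusion.** The point holds in this form: the label is applied to the trial as a whole, while the procedures described do not deliver blinding for the patient. Its reach is 7 of 7 comparisons in the SAP, with grafting-site pain less directly exposed and ibuprofen partly protected in measurement. Its size in bias terms is unknown, and the documents give no basis for estimating it.

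The conclusion rests on the sections cited describing the blinding steps fully, and on patients being able to notice and interpret the draw. The first can be read from the text; the second is an inference that the approved patient information could overturn. The blinded assessment of donor-site healing is not affected. The point should be corrected because it concerns a headline design property and the remedy is cheap.

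**What to change.** In the Study design section, replace the double-blinded label with masking status by role:

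- donor-site healing evaluator and data analyst: blinded;
- blood-collection operator: aware of allocation from before surgery;
- surgeons: unaware until the second envelope is opened, after harvesting and before the palatal wound is covered;
- patients: not assured to be masked, because blood is drawn in the Test Group only, unless the sponsor documents how they were masked and what they were told about the draw.

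State alongside the SAP analyses that conclusions on the VAS items and ibuprofen use are open to expectation and reporting bias of unknown size and direction, noting the lesser exposure of grafting-site pain. Leave the statement on blinded healing assessment as it is.

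The cost is a change of wording and a sponsor check of the approved patient information, with no added visits, procedures, tests or patients. The change does not remove any bias. The downside is a less favourable design label and more cautious conclusions on the patient-reported outcomes and analgesic use.
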